#### 5.4.2.3 Example of Specimen Label Generated by STS

STS includes a label printing facility, accessed via the Print Label CRF in the All Specimens folder. A generated PDF is emailed to the user as a result of saving that form.

The following image is an example of a tissue specimen label printed on a label that is 0.5" high and 1.28" wide.

The QR code in the above example is for the Specimen ID shown on the second line.

Labels may be printed on a special purpose label printer, one label at a time, or on a standard laser printer, multiple labels per page. Theradex recommends the use of these low temperature waterproof labels for standard laser printers: <https://www.labtag.com/shop/product/cryo-laser-labels-1-28-x-0-5-cl-23-colors-available/>

The last line item on the label includes the following data points joined together:

1. Tissue only: Primary (P), Metastatic (M), Normal (N) tissue indicated at the beginning of the specimen ID; this field is blank if not relevant (e.g., for blood)
2. Block ID or blank if not relevant
3. SPID (Surgical Pathology ID) or blank if none
4. An optional alpha-numeric code that is protocol specific and is only included if the protocol requires an additional special code classification

**Space is provided at the bottom of the label for the handwritten date and optional time.**  
The last line on the example label is for the handwritten date and optional time.

#### 5.4.3 Overview of Process at Treating Site

##### 5.4.3.1 OPEN Registration

All registrations will be performed using the Oncology Patient Enrollment Network (OPEN) system. OPEN communicates automatically with the Interactive Web Response System (IWRS) which handles identifier assignments, any study randomization, and any prescribed slot

assignments. If specimen analysis is required to determine eligibility, the protocol will be setup with multi-step registration.

Registration without eligibility specimen analysis:

1. Site enters registration data into OPEN during one or more steps.
2. IWRS receives data from OPEN, generates the Patient Study ID and the Universal Patient ID, both of which are sent back to OPEN.
3. IWRS sends all applicable registration data directly to Rave at the end of the final registration step.

Any data entry errors made during enrollment should be corrected in Rave.

#### 5.4.3.2 Rave Specimen Tracking Process Steps

**Step 0:** Log into Rave via your CTEP-IAM account, then navigate to the appropriate participant.

**Step 1:** Complete the **Histology and Disease** form (but do not upload reports until a specimen label can be applied to them) and the Baseline forms regarding **Prior Therapies**. Enter the initial clinical specimen data:

- **Specimen Tracking Enrollment** CRF: Enter Time Point, Specimen Category, Specimen Type, Block number, Tissue type, Surgical Path ID, and number of labels needed (include extra labels to apply to reports to be uploaded). CRF generates unique Specimen ID.

**Step 2:** Print labels using the Print Labels CRF located in the All Specimens folder, then collect specimen.

- Label specimen containers and write collection date and time on each label. After collection, store labeled specimens as described in Section 5.4.2.
- Apply an extra specimen label to each report before scanning. Return to the **Histology and Disease** form to upload any initial Pathology, Radiology, Molecular Reports (up to 4), Surgical (or Operative) reports and Tissue Biopsy Verification form (when applicable). Return to **Specimen Tracking Enrollment** CRF to upload any molecular report (one per specimen) and/or specimen specific pathology or related report (one per specimen). Uploaded reports should have protected health information (PHI) data, like name, date of birth, mailing address, medical record number or social security number (SSN), redacted. Do not redact SPID, block number, diagnosis or relevant dates (such as collection date), and include the UPID and patient study ID on each document.

**Step 3:** Complete specimen data entry.

- **Specimen Transmittal** Form: Enter collection date and time and other required specimen details.

**Step 4:** When ready to ship, enter shipment information.

- **Shipping Status** CRF: Enter tracking number, your contact information, recipient,

number of sample containers and ship date once for the first specimen in a shipment.

- **Copy Shipping** CRF: In the specimen folders for additional specimens (if any) that will be shipped with the initial specimen, please use the **Copy Shipping** form to derive common data into additional **Shipping Status** forms. A few unique fields will still need to be entered in **Shipping Status**.

**Step 5:** Print shipping list report and prepare to ship.

- Shipping List report is available at the site level.
- Print two copies of the shipping list, one to provide in the box, the other for your own records.
- Print pathology or other required reports to include in the box. Be sure the printed copy includes the specimen label.

**Step 6:** Send email notification.

- For only one of the specimens in the shipment, click “Send Email Alert” checkbox on the **Shipping Status** CRF to email recipient.

**Step 7:** Ship the specimen(s).

**Step 8:** Monitor the Receiving Status form located in each specimen folder for acknowledgment of receipt and adequacy.

## 5.5 Specimen Collection

### 5.5.1 Archival or Formalin-Fixed Paraffin-Embedded (FFPE) Tumor Specimen

**A copy of the corresponding anatomic pathology report must be sent with the Archival tissue and uploaded to Rave.**

If previously-collected FFPE tissue will be submitted, then the following criteria must be met:

- Tissue must have been collected within 6 months prior to registration
- FFPE tumor tissue block(s) must be submitted. The optimal block is at least 70% tumor. Specimen size requirement is as follows:
  - Surface area: 25 mm^2 is optimal. Minimum is 5 mm^2.
  - Volume: 1 mm^3 optimal. Minimum volume is 0.2 mm^3, however the success of DNA extraction decreases at suboptimal tissue volume.

If an existing block cannot be submitted, the following are requested, if available:

- Twenty to twenty-five (20 – 25) 10 µm unstained air-dried uncharged slides (Patients may be enrolled if a minimum of the first 20 slides are available); uncharged slides at 10-microns (µm) are preferred for slides intended for DNA/RNA extractions (mandatory).
- Ten (10) 4 µm unstained air-dried charged slides (optional)

Process and number slides sequentially (e.g., unstained slides should be processed and be labeled 1 – n).

See Section 5.4.2 for labeling instructions.

### **5.5.2 Formalin-Fixed Tumor Biopsies**

**The Tissue Biopsy Verification Form (Appendix E), a copy of the radiology and/or operative reports from the tissue removal procedure and the diagnostic anatomic pathology report must be sent with the tissue and uploaded to Rave.**

1. Label formalin-filled containers according to instructions in Section 5.4.2.
2. Obtain fine needle aspirate (FNA) and submit to pathology for review. Rapid On-Site Evaluation (ROSE) by a cytopathologist should be used, when available, to confirm placement in viable tumor.
3. Obtain 2-3 16-gauge or 18-gauge core needle biopsy specimens, and place one core in each cassette.
4. Snap the cassette lids closed and place cassettes into a formalin-filled pre-labeled container as soon as possible after collection to prevent air drying. Up to two cassettes may be placed in one formalin jar.
5. Secure the container lids and package containers into the shipping kit according to instructions in Section 5.6. Keep tissue in formalin jars at room temperature until shipment to the EET Biobank.

### **5.5.3 Blood Collection**

#### **5.5.3.1 Collection of Blood in Streck cfDNA Tube (EET Biobank)**

1. Label two 10 mL Streck cfDNA tubes according to the instructions in Section 5.4.2.
2. Collect 10 mL of blood into each pre-labeled tube and gently invert to mix. **Note:** blood must be thoroughly mixed to ensure preservation of specimen. Heparin should be avoided in pre-collection flush procedures. If therapeutic heparin dosing contamination is a possibility, then venipuncture is recommended as a first choice collection method. If a Streck cfDNA tube immediately follows a heparin tube in the draw order, then collecting an EDTA tube as a waste tube prior to collection in the Streck Cell-Free DNA BCT is recommended.
3. **After collection, blood in Streck cfDNA tubes should never be refrigerated**, as this will compromise the specimen. Blood collected in Streck cfDNA tubes is stable at room temperature.

#### **5.5.3.2 Collection of Blood in Sodium Heparin Tubes ([name] laboratory)**

1. Label sodium heparin (green top) tubes according to the instructions in Section 5.4.2.
2. Collect 10 mL of whole blood in sodium heparin (green top) tubes (6 tubes total).
3. Collected at C1D1, C2D1, C3D1, C4D1, and at disease progression.

### 5.5.3.2.1 Tubes processing procedure at time of collection

Please contact the Protocol Contact if local standard operating procedure (SOP) for PBMC isolation requires deviation from these instructions.

#### Equipment/Supplies

1. 50mL Leucosep tubes
2. Ficoll-Paque PLUS (Amersham Biosciences, Cat. # 17-1440-03)
3. 5mL and 10mL sterile pipettes, individually wrapped
4. 50mL polypropylene tubes (sterile)
5. 15mL polypropylene tubes (sterile)
6. 1.8mL cryotube vials
7. Controlled rate freezing containers (Nalgene "[name]")
8. -80°C Freezer
9. Hemocytometer

#### Reagents

1. Fetal Bovine Serum (Gibco)
2. Dulbecco's Phosphate-Buffered Saline
3. DMSO (Cat# D2650, endotoxin tested, Sigma)
4. Trypan Blue for cell counting

#### Standards and Calibration

### **Procedure**

The desired quantity of peripheral blood mononuclear cells (PBMC) is around 8 million cell per vial plus 2 vials for flow cytometry (FACS) at around 2.0-2.4 million cells per vial.

- A. Preparation of Ficoll paque /leucosep tube
  1. Pipette 15ml of Ficoll into each of the 50ml Leucosep tubes.
  2. Centrifuge at 1000 RCF for 30s, then store in the dark at room temperature.
- B. PBMC isolation, aliquoting and freezing
  1. Pipette whole blood onto the membrane frit of the Leucosep tube. (No more than 30ml of whole blood in each Leucosep tube.)
  2. Centrifuge at 1000 RCF for 10 minutes
  3. If possible, pipette and save up to 12 mL of plasma from the top layer. Place plasma in 15 ml conical tube and place in -80°C.
  4. Pipette away the buffy-coat PBMC inter-phase layer and the overlaying plasma with a 5ml pipette. (You may have to gently scrape the side of the tube with the pipette tip to remove adherent PBMC, and be careful that you do not pipette any of the underlying Ficoll.)
  5. Transfer buffy-coat into 2 new 50ml tubes and fill each to 45 ml with PBS + 10% FBS.
  6. Centrifuge the 50ml tubes with the buffy-coat at 250 RCF for 10 minutes

7. Carefully decant the supernatant into a container with bleach (beware of splashing bleach) and re-suspend the pellets containing the PBMC in a total of 25ml of PBS in a single 50ml tube.
8. Keep a small aliquot for counting
9. Centrifuge at 250 RCF for 10 minutes
10. Determine the number of cryovials needed (see below, Calculations to Determine # Cryovials)
11. Decant supernatant into bleach.
12. Count cryovials and divide the # by 2. This is the number of mL of FBS used to re-suspend the cell pellet
13. Re-suspend pellet in FBS.
14. Draw 1ml of suspension.
15. Place  $\frac{1}{4}$  of above into a new 15ml tube.
16. Place  $\frac{3}{4}$  back into the original 50ml tube.
17. Discard pipette.
18. Draw 1ml of FBS.
19. Place  $\frac{1}{4}$  into re-suspension (original 50mL tube).
20. Place  $\frac{3}{4}$  into the 15ml tube.
21. Using a new pipette, obtain the same number of ml as step 14 of 20% DMSO in FBS.
22. Add drop wise (while gently swirling the tube) to the re-suspension in the 50ml tube.
23. Place 1ml of the re-suspension into each cryovial.
24. Add 1ml of DMSO into the 15ml tube (drop wise/swirl)
25. Pipette the cell suspension to FACS vials, 1 ml each.
26. Place the cryovials + FACS vials in a freezing containers
- 27. Place in -80°C freezer for at least an overnight period (12 hours), then transfer to liquid Nitrogen freezer. Samples should be shipped in batch, quarterly.**

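### The PBMC freezing steps 12, 21, 23 and 24 do not reconcile: read literally, the main tube runs short for more than two cryovials and the flow-cytometry vials reach 50% DMSO

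*Combined protocol and SAP*

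**What the plan says.** The procedure aims for "around 8 million cell per vial plus 2 vials for flow cytometry (FACS) at around 2.0-2.4 million cells per vial". The calculation that follows it sets the number of regular vials, B, as total PBMC divided by 8 million.

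The relevant steps of part B are:
- Step 12: "Count cryovials and divide the # by 2. This is the number of mL of FBS used to re-suspend the cell pellet".
- Steps 14 to 16: "Draw 1ml of suspension"; a quarter goes to a 15 mL tube and three quarters return to the 50 mL tube.
- Steps 18 to 20: "Draw 1ml of FBS"; a quarter goes to the 50 mL tube and three quarters to the 15 mL tube.
- Steps 21 and 22: "obtain the same number of ml as step 14 of 20% DMSO in FBS", added to the 50 mL tube.
- Step 23: "Place 1ml of the re-suspension into each cryovial".
- Step 24: "Add 1ml of DMSO into the 15ml tube (drop wise/swirl".
- Step 25: 1 mL of the 15 mL tube's contents goes into each flow-cytometry vial.

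The reagent list names DMSO as a bottled product and lists no 20% stock. No section states a final DMSO concentration. The opening of Section 5.5.3.2.1 asks sites to get in touch if their own procedure "requires deviation from these instructions".

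Sections 5.1 and 5.5.3.2 call for six 10 mL tubes at C1D1, C2D1, C3D1, C4D1 and progression. Collection is mandatory. Section 5.8 classes both assays, flow cytometry and ELISpot, as exploratory.

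**The concern.** Step 21 describes a matching volume but points to a step with a fixed 1 mL. The step with a volume that depends on the number of vials is step 12. Step 24 drops the dilution that step 21 spells out, so its plain reading is undiluted DMSO. A technician who follows the text exactly cannot fill the planned vials once B exceeds 2, and would freeze the two kinds of vial at very different DMSO concentrations.

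At stake are the blood-based immune data for exploratory objective 1.3.4, which includes change over treatment. A pre-treatment sample cannot be drawn again. Vials are shipped in quarterly batches, so a problem may not reach the receiving laboratory for some months. If some sites quietly repair the steps and others follow them, freezing conditions would differ by site for reasons unrelated to the patients.

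**Working it through.** **Inputs.** All come from Section 5.5.3.2.1 (Procedure, part B, and the cryovial calculation), except B, which the documents do not give. Let A be total PBMC, so that A = 8 million × B.

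**1. The plan's own cell counts reproduce.** Cells in both flow-cytometry vials: C = [A/(0.5B)] × 0.25 = (8 million × B)/(0.5B) × 0.25 = 4.0 million, or 2.0 million per vial. That is the lower end of the stated 2.0-2.4 million. Each regular vial holds (A − C)/B = 8 − 4/B million, for example 7.5 million at B = 8, which fits the target of around 8 million. The formula matches steps 12 to 15: a pellet in B/2 mL, with 0.25 mL removed. Its regular-vial figure assumes that all B vials are filled.

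**2. Volumes before any DMSO.**
- 50 mL tube: B/2 − 0.25 + 0.25 = B/2 mL.
- 15 mL tube: 0.25 + 0.75 = 1.0 mL.

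**3. 50 mL tube as written.** Step 21 adds 1 mL at 20%.
- Volume available: B/2 + 1 mL. Volume needed: B mL. Shortfall: B/2 − 1 mL, which is zero at B = 2 and positive above it.
- DMSO concentration: 0.2/(B/2 + 1).
- Cells per filled 1 mL vial: (A − C)/(B/2 + 1).

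| Assumed B | mL available | mL needed | DMSO | Vials filled | Million cells per filled vial | Planned (8 − 4/B) |
|---|---|---|---|---|---|---|
| 2 | 2.0 | 2 | 10% | 2 of 2 | 6.0 | 6.0 |
| 4 | 3.0 | 4 | 6.7% | 3 of 4 | 9.3 | 7.0 |
| 6 | 4.0 | 6 | 5.0% | 4 of 6 | 11.0 | 7.3 |
| 8 | 5.0 | 8 | 4.0% | 5 of 8 | 12.0 | 7.5 |
| 10 | 6.0 | 10 | 3.3% | 6 of 10 | 12.7 | 7.6 |
| 15 | 8.5 | 15 | 2.4% | 8 of 15 | 13.6 | 7.7 |

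The span from 4 to 15 corresponds to an assumed yield of 0.5 to 2 million PBMC per mL from 60 mL of blood: A = 30 to 120 million, and A/8 million = 3.75 to 15.

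**4. 15 mL tube as written.** 1.0 mL + 1 mL undiluted DMSO = 2.0 mL at 1/2 = 50%. The share of cells exposed is C/A = 0.5/B: 8.3% at B = 6 and 5% at B = 10.

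**5. The reading that closes.**
- Step 21 takes the step 12 volume: B/2 + B/2 = B mL at 0.2 × (B/2)/B = 10%, for every B.
- Step 24 uses the 20% mix: 1.0 + 1 = 2.0 mL at 0.2/2.0 = 10%, exactly two 1 mL vials.

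Both vial types then match, and the cell counts in item 1 are met. A likely cause of the step 21 error is a stale cross-reference: part A has two steps, so step 12 of part B is the 14th if the two parts are numbered continuously.

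**The case against.** The strongest reply is that the text nearly reveals its own meaning. Asking for the same number of mL makes little sense for a fixed 1 mL and echoes step 12. DMSO in step 24 can be shorthand for the 20% mix named three steps earlier. The volume error also announces itself, because the operator knows B in advance and runs out while dispensing. Section 5.5.3.2.1 gives sites a route to raise differences, both assays are exploratory, and Section 9.3 plans only descriptive summaries of exploratory biomarkers. Objective 1.3.4 also draws on tissue immune markers that use no PBMC.

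Most of this stands, and it limits severity. It does not remove the error: a site that runs out of suspension must improvise, and the step 24 ambiguity gives no warning, because the volume comes to 2.0 mL on either reading.

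Four stronger readings are tempting but unsupported:
- **All the blood is compromised.** Five 60 mL draws make 300 mL per patient, but only about 0.5/B of the cells could meet 50% DMSO. The rest go into fewer, denser vials and are not lost for want of volume.
- **The regular vials are under-filled.** Step 23 puts 1 mL in each vial used; the later vials stay empty.
- **The cells will be damaged.** The documents say nothing about the effect of 2-7% or 50% DMSO on recovery or assay results.
- **Literal use is enforced.** The sentence about deviations foresees that local procedures may differ and says whom to contact.

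**Conclusion.** Wrong as written; minor severity. The shortfall of B/2 − 1 mL for every B above 2 follows from the steps themselves and needs no assumption about DMSO toxicity. The numbers of unfilled vials rest on assumed values of B: 2 of 6, or 4 of 10. The 50% figure rests on reading step 24 as undiluted DMSO, which is the plain reading but not the only one. The 10% figure is inferred from the way the volumes close and is not a protocol target. What the documents establish is a procedure that cannot be carried out as planned for B above 2 and that leaves the two vial types at different concentrations. They do not establish that samples will be unusable. The MTD, safety and PFS endpoints do not depend on these samples.

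**What to change.** Ask the receiving laboratory to confirm the recipe first, since the intended concentration is an inference. If it agrees:
- Step 21: refer to the volume of step 12 in place of step 14.
- Step 24: specify 1 mL of the 20% DMSO in FBS used in step 21.
- State the final DMSO concentration once, for both vial types, so that sites can check their volumes.
- Send sites a short correction notice.

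The cost is a few words and one notice, with no extra blood, visits or assays. For samples already frozen, ask sites which reading they used and record it with the sample, so that freezing conditions can be considered when the immune data are summarised.

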#### Calculation to Determine Number of Cryovials

Number of cell counted  $\times$  5  $\times$  total volume of the suspension  $\times$  10,000 = A (Total PBMC)

A / 8,000,000 = B (number of vials you want)

[A / (.5  $\times$  B)]  $\times$  0.25 = C (Total number of PBMC in both FACS vials)

A – C = D (number of lymphocytes left after FACS lymphocytes removed)

D / B = number of lymphocytes in each regular vial

#### 5.5.3.3 Collection of Blood in Sodium Heparin (Green Top) Tubes for Entinostat PK (JHU APC)

1. Label sodium heparin (green top) tubes according to the instructions in Section 5.4.2.
2. Obtain venous blood by standard phlebotomy technique from a peripheral access point (Central access is permissible since entinostat is administered orally).
3. Collect 4 mL of whole blood in sodium heparin (green top; e.g. BD 367871 or 367884) tubes (1 tube total).
4. Invert each tube several times (8-10 times) immediately after collection.
5. Place samples immediately **on ice** after collection; samples must be processed **within 30 minutes**.

6. Collected at time points listed in section 5.1

5.5.3.3.1 Processing of Blood in Sodium Heparin (Green Top) Tubes for Entinostat PK (JHU APC)

1. Invert sample 8-10 times immediately before processing.
2. Centrifuge at ~1200xg for 10 minutes in swinging bucket (SW) or 15 minutes in a fixed angel (FA) rotor at 4°C in a refrigerated centrifuge. Make sure that the centrifuge reaches speed and is maintained throughout the entire spin.
3. Carefully remove tube from centrifuge.
4. Using a pipette, transfer equal aliquots of plasma into 2-3 labeled 1.2 mL cryovials (e.g., preferred are external thread, conical self-standing vials like CorningTM 430658), not exceeding ~1 mL per cryovial.
5. Label samples per Section 5.4.2.1 above.
6. Store plasma samples at -70°C or below until shipment or transfer to Johns Hopkins.

5.5.3.4 Collection of Blood in Serum (Red Top) Tubes for Atezolizumab PK (OSUCCC PhASR)

1. Venous whole blood (6 mL) will be collected into pre-labeled serum (red-top; e.g. BD 367815 or 368660) tubes at the time points specified. Collect each PK sample as close as possible to the planned (nominal) time relative to dosing.
2. Collected at time points listed in section 5.1
3. If a cannula is used, the cannula will be inserted into an arm vein within sufficient time prior to dosing, kept patent with normal saline or heparin solution, and will be removed as instructed by physician or earlier if the subject requests. To avoid artificial dilution of the PK samples by saline, 1 mL of whole blood will be collected and discarded before each whole blood PK sample is collected.

5.5.3.4.1 Processing of Blood in Serum (Red Top) Tubes for Atezolizumab PK (OSUCCC PhASR)

1. Allow blood to clot upright at room temperature for at least 30 minutes (maximum 60 minutes) prior to processing.
2. If the blood is not immediately processed after the clotting period, then tubes should be stored (after the 30-60 minutes of clotting time) at 4°C for no longer than 4 hours.
3. Centrifuging for 10 minutes at 1,200 × g at room temperature.
4. Using a clean transfer pipette, aliquot serum into the labeled cryovials (~2-3) at an aliquot volume of 1 mL per tube. Labeling should be printed from the ETCTN Specimen Tracking System (label should include at a minimum the Study ID, Patient ID, sample type, sample collection date, exact sample collection time).
5. Avoid picking up red blood cells when aliquoting by keeping the pipet above the red blood cell layer and leaving a small amount of serum in the tube.

6. Tightly secure the cap of the vials before storage.
7. Aliquoting and freezing of serum specimens should be completed within 1 hour of centrifugation.
8. Store serum cryovials upright in a specimen box or rack in a -70°C to -90°C or colder freezer. Do not allow specimens to thaw after freezing.

## 5.6 Shipping Specimens from Clinical Site to the EET Biobank

### 5.6.1 General Shipping Information

When kits are provided, the shipping container sent with kit contents should be used to ship specimens to the EET Biobank. In winter months, please include extra insulation, such as bubble wrap, inside the shipping container.

**For formalin-fixed biopsies, the Tissue Biopsy Verification Form (Appendix E) and a copy of the radiology and/or operative reports from the tissue removal procedure and the diagnostic anatomic pathology report must be sent with the tissue to the EET Biobank.**

**For all archival tissue, the corresponding anatomical clinical pathology report is required both in the package and uploaded in the ETCTN specimen tracking system.** If this is not available at the time of shipment, then it must be sent to the EET Biobank as soon as possible and uploaded to the ETCTN specimen tracking system, or the specimen will not be processed. The pathology report must state the disease diagnosis made by the reviewing pathologist.

